16. EFFICACY OUTCOMES

Analyses of efficacy outcomes are based on EAS except PFS and OS, which are estimated based on SAS.

16.1. PRIMARY EFFICACY VARIABLE(S) & DERIVATION(S)

16.1.1. BEST OVERALL RESPONSE (BOR)

BOR will be determined using time point responses (TPRs) up until the last evaluable TPR prior to or on the date of (i) disease progression as defined by RECIST Version 1.1 (Eisenhauer et al., 2009) or death; or (ii) withdrawal of consent; or (iii) receiving subsequent anti-cancer therapy, whichever is earlier.

The timing of an overall TPR will always be derived based on scan dates not response assessment dates. For a scheduled tumor scan assessment, it is expected that there may be a variation for the actual timing of scans among target, non-target, and new lesions. In assigning a date for the overall response assessment at a visit, the earliest date collected at that visit will be used. Within a grouped timepoint, if there are multiple assessments on different dates for the same target lesions, the last assessment will be used.

A patient's BOR will be determined based on [APPENDIX 3](#).

Document: [REDACTED]

Author: [REDACTED]

Version Number:

2.5

Version Date:

18Feb2022

Template No.: [REDACTED]

Reference: CS_WI_BS005

Effective Date: 02Dec2019

There are two ways of assigning BOR for a patient when the minimum interval for confirmation of CR and PR is not satisfied or if there are no confirmatory scans for CR and PR:

- Adding two more response categories as: unconfirmed CR, unconfirmed PR.
- Assigning BOR as SD, that is, both the unconfirmed CR and unconfirmed PR will be SD.

Both ways of assigning BOR will be implemented.

The number and percentage of patients in each category of derived BOR (Confirmed CR, Confirmed PR, SD, PD, or NE) will be summarized.

16.1.2. OBJECTIVE RESPONSE RATE (ORR)

Objective response rate (ORR) will be calculated using two different ways:

- Scenario #1: ORR will be calculated using a strict interpretation of RECIST Version 1.1. Objective response will be derived as no/yes variable. Patients with a BOR of confirmed CR or PR will be assigned ‘Yes’. Patients not having a BOR of confirmed CR or PR will be assigned ‘No’. Hence, ORR is defined as the proportion of patients with objective response being “Yes”.
- Scenario #2: ORR_{UNCONFIRMED} will be calculated using all responses regardless of confirmation. Objective response will be derived as no/yes variable. Patients with a BOR of confirmed CR, confirmed PR, unconfirmed CR or unconfirmed PR will be assigned “Yes”. All patients with other BOR values will be assigned “No”. Hence, ORR_{UNCONFIRMED} is defined as the proportion of patients with objective response being “Yes”.

16.1.3. DURATION OF RESPONSE (DOR)

The DoR is defined as the time from the date of the first objective response (CR or PR which is subsequently confirmed) until the date of the documented progression or of death, whichever comes first. DoR will only be analyzed for patients whose BOR is either CR or PR. Censoring will follow the rules outlined below for PFS in [Section 16.1.5](#).

16.1.4. DURATION CONTROL RATE (DCR)

The DCR is defined as the percentage of patients in EAS with a BOR of confirmed CR, confirmed PR or SD for 7 weeks.

16.1.5. PROGRESSION FREE SURVIVAL (PFS)

The PFS is defined as the time from date of first dosing until the date of an objective disease progression as defined by RECIST Version 1.1 (Eisenhauer et al., 2009) or death due to any cause, whichever comes first. More specifically, PFS will be determined using all the assessment data up until the last evaluable visit prior to or on

Document:	[REDACTED]		
Author:	[REDACTED]	Version Number:	2.5
		Version Date:	18Feb2022
Template No.:	[REDACTED]	Reference:	CS_WI_BS005
Effective Date:	02Dec2019		

the date of (i) disease progression as defined by RECIST Version 1.1 or death; or (ii) withdrawal of consent; or (iii) receiving subsequent anti-cancer therapy, whichever is earlier.

The rule of censoring/ event is summarized in Table 1.

The PFS time will always be derived based on scan dates not tumor assessment dates. If PD is documented between scheduled visits, the actual date of documented progression will be used as an uncensored value in the analysis of PFS.

RECIST assessments/scans contributing towards a particular visit may be performed on different dates. The following rules will be applied:

- Date of progression will be determined based on the earliest of the dates of the component that triggered the progression.
- When censoring a patient for PFS the patient will be censored at the latest of the dates contributing to a particular overall visit assessment.

Table 1 Progression free survival

Description	Event/ Censor	Date of Event/Censor
Documented progression before starting use of new anticancer treatment and without missing two consecutive tumor assessment visits	Event	Date of first documented disease progression
Death without progression	Event	Date of death
Progression or death after two or more consecutive missed tumor assessments	Censor	Date of last adequate tumor assessment before two consecutive missed tumor assessment visits
No evaluable baseline tumor assessment	Censor	Date of first dosing of study treatment
No evaluable tumor assessment after first dose of study treatment	Censor	Date of first dosing of study treatment
New anticancer treatment started prior to documented disease progression or death on study	Censor	Date of last evaluable tumor assessment before start use of new anticancer treatment/two consecutive missed tumor assessment visits
No progression and no death before end of study or data cut-off	Censor	Date of last evaluable tumor assessment
Note: An adequate radiologic assessment is defined as an assessment where the Investigator determined radiological response is CR, PR, SD, or PD. If PD and new anti-cancer therapy occur on the same day, will assume that the progression was documented first, e.g. outcome is progression and the date is the date of the assessment of progression.		

Document: [REDACTED]

Author: [REDACTED]

Version Number:

2.5

Version Date:

18Feb2022

Template No.: [REDACTED]

Reference: CS_WI_BS005

Effective Date: 02Dec2019

Note: Two consecutive scheduled tumor assessments is equal to 126 days (=2* (8 weeks *7+ 7 days)) since previous evaluable RECIST 1.1 or baseline assessment if there is no post baseline tumor assessment.

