### **Progression Free Survival (PFS)**

Progression free survival is defined as the time from date of first dose of study drug until the date of an objective disease progression as defined by RECIST v1.1 or death due to any cause.

Patients who have not objectively progressed or died by the date of the analysis cut-off or received any further antitumor therapy will be censored at the time of the last evaluable objective tumor assessment before the cut-off date or the antitumor therapy start date.

Progression-free survival rate is defined as the percentage of patients without evidence of progression or death at specific time points, such as week 12 (cohorts B and C), week 16 (cohort D and E) on study.

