### **Baseline Disease Assessment**

All baseline evaluations should be performed as closely as possible to the beginning of treatment and never more than 4 weeks before the beginning of the treatment.

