4.2. SAFETY ANALYSIS SET [SAS] – (ALL TREATED POPULATION)

The analysis set includes all patients who have received at least one dose of fruquintinib. Patients in the SAS will be analyzed by their actual dose initially received. If patients have dose reduction during the study, all data will be summarized/analyzed on the initial dose of study drug received.

All safety analyses except for DLT summaries, along with PFS and OS will be based on the SAS.

If there is any doubt whether a patient was treated or not, they will be assumed treated for the purpose of analysis.

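### SAP Table 1 gives a death without an evaluable scan two conflicting PFS outcomes, event at death or censored at first dosing, and states no precedence

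*SAP*

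**What the plan says.** SAP 16.1.5 defines PFS from first dose to RECIST progression or death from any cause. Table 1 then lists the event and censoring rules. Three rows matter here:

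- "Death without progression": event, dated at death. The row does not require that a scan exists.
- "No evaluable tumor assessment after first dose of study treatment": censored at the date of first dosing. The row has no exception for death.
- "No evaluable baseline tumor assessment": also censored at first dosing, again with no exception for death.

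A further row censors progression or death that follows two or more consecutive missed assessments. Its note sets that interval at 126 days, counted "since previous evaluable RECIST 1.1 or baseline assessment if there is no post baseline tumor assessment". The only tie-break in the table or its notes is for progression and new therapy recorded on the same day.

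On the analysis set, SAP 4.2 says "All safety analyses except for DLT summaries, along with PFS and OS will be based on the SAS", meaning all treated patients. Protocol 2.2.2 makes the PFS rate the primary endpoint of the expansion phase (SAP 2.3.2 calls it PFS). SAP 16.2 estimates the rate by Kaplan-Meier. Protocol 8.5 names the landmarks as "week 12 (cohorts B and C), week 16 (cohort D and E) on study" and assigns censoring to "Patients who have not objectively progressed or died by the date of the analysis cut-off" or who received further antitumor therapy.

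**The concern.** A treated patient who dies before any evaluable post-baseline scan satisfies the first row and the second. A patient who had no evaluable baseline scan and then dies satisfies the first row and the third. The two outcomes are opposites: one counts a failure, the other removes the patient from the risk set at time zero.

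The case is not empty by construction. Using the all-treated set brings unscanned patients into the PFS analysis, and the definition of the Efficacy Analysis Set in SAP 4.4 itself provides for patients who die of their disease before a first post-baseline scan.

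Two programmers could each follow Table 1 faithfully and report different primary PFS rates. The study has one arm per cohort and no formal hypothesis test (SAP 5.5), so the estimated rate is itself the result. A reading that leaves early deaths out of it makes the drug look better.

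**Working it through.** **The plan's own figures.** The 126-day interval reproduces: 2 × (8 × 7 + 7) = 126. The planned precision also reproduces. The exact 95% interval for 20/40 is 0.338 to 0.662 (Table 16: 0.34 to 0.66), and for 6/15 it is 0.163 to 0.677 (Table 15: 0.16 to 0.68).

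**Inputs.** Cohorts B and C have n = 40 and Cohorts D and E have n = 15 (protocol 8.6). The landmarks are week 12 for B and C and week 16 for D and E (protocol 8.5). The documents give no number of unscanned deaths and no expected PFS rate, so d (unscanned deaths before the landmark) and x (patients progression-free at the landmark) are assumptions.

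**No other early censoring.**

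- Deaths as events: rate = x/n.
- Deaths censored at first dosing: rate = x/(n − d).
- Ratio: n/(n − d).

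| n, landmark | x | d | event | censored | ratio |
|---|---|---|---|---|---|
| 40, week 12 | 18 | 1 | 18/40 = 45.0% | 18/39 = 46.2% | 40/39 = 1.026 |
| 40, week 12 | 18 | 2 | 18/40 = 45.0% | 18/38 = 47.4% | 40/38 = 1.053 |
| 15, week 16 | 6 | 1 | 6/15 = 40.0% | 6/14 = 42.9% | 15/14 = 1.071 |

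**With other censoring.** Let Y be the number at risk when the deaths are events, Y0 the number at risk when they are censored at first dosing, and R the ratio of the two Kaplan-Meier estimates (censored over event). Follow Q = R × Y/Y0 through time.

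- At the start, Q = n/(n − d).
- At another patient's event, R is multiplied by (Y0 − 1)Y / [Y0(Y − 1)] and Y/Y0 by the reciprocal, so Q is unchanged.
- At an unscanned death, R is multiplied by Y/(Y − 1) and Y/Y0 by (Y − 1)/Y, so Q is unchanged.
- At another patient's censoring, R is unchanged and Y/Y0 becomes (Y − 1)/(Y0 − 1), which is no smaller because Y ≥ Y0. Q cannot fall.
- At the landmark all d deaths have occurred, so Y = Y0 and R = Q.

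Hence R is at least n/(n − d) for any non-zero rate.

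**Limit of the direction claim.** It applies to deaths before the landmark. A patient who dies unscanned after the landmark but inside the 126 days is progression-free at the landmark under the event reading, and censoring that patient lowers the rate, for example from 18/40 = 45.0% to 17/39 = 43.6%.

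**Does other text settle the conflict?**

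- The PFS definition counts death from any cause. That favours an event.
- Protocol 8.5 does not censor a patient who has died without further therapy. That favours an event. But Table 1 already departs from protocol 8.5 by censoring deaths after missed assessments, so protocol 8.5 cannot decide the matter alone.
- The 126-day note starts at baseline when there is no post-baseline scan. It would serve little purpose if every such patient were censored at first dosing regardless. That favours an event, but the note does not say that it overrides the row on missing scans.
- SAP 2.4 lists the move of PFS out of the Efficacy Analysis Set and declares no change in how deaths are handled.

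**The case against.** The best answer is that the intent is plain. Three texts lean the same way, the SAP presents Table 1 as a summary of a rule whose definition already includes death, and a careful programmer would choose the event. This largely stands: the censoring reading is the weaker one. A reader might infer that the SAP deliberately drops early deaths from the primary analysis. The documents do not support that. They show two rules without an order, and most of the surrounding text points away from censoring. What does not stand is the step from intent to rule, because no sentence gives the death row priority.

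The second answer is size, and this stands too. Eligibility requires expected survival above 12 weeks (protocol 4.1, criterion 9). The first post-baseline scan is due on day 29 (Cohorts A and B) or day 57 (Cohorts C to E), and protocol 6.4 asks for a scan at treatment completion, with exceptions. The row for a missing baseline scan should be nearly empty, since a screening tumor assessment is scheduled and criterion 7 requires measurable disease or bone lesions.

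A reader might also infer that the 126-day clock itself is faulty and should always start at first dose. Baseline evaluation may be up to 28 days early ("never more than 4 weeks before the beginning of the treatment", protocol Appendix C). From day −28, 126 days end on study day 99, before week 16 (day 113). But the baseline start is an explicit rule, and the conflict can be resolved without touching it. Moving it would also change results more widely. Take a Cohort B or C patient scanned on day −28 who dies unscanned on day 110. The present missed-assessment row censors that patient. With the clock moved, the patient is an event on day 110 and progression-free at week 12, so with 18 others progression-free the rate goes from 18/39 = 46.2% to 19/40 = 47.5%. That is a separate change of analysis, and this point does not call for it.

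**Conclusion.** The conflict is real and bears on the primary endpoint. Table 1 gives the same patient two outcomes with no stated order, and the all-treated analysis set keeps such patients in the analysis. For deaths before the landmark, the censoring reading always raises a non-zero rate, by at least n/(n − d).

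The practical size is probably small. In the illustrations the shift is 1.2 or 2.4 percentage points for one or two deaths in 40, and 2.9 points for one death in 15. The planned intervals are far wider: 0.34 to 0.66 at 20/40 and 0.16 to 0.68 at 6/15. The illustrations rest on assumed counts and no other early censoring; with other censoring the ratio is the same or larger. This should be corrected because the primary result ought to be reproducible from its own rules. It does not by itself put the study's conclusions in doubt.

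**What to change.** Add to Table 1 that death without documented progression is an event on the date of death even if there is no evaluable baseline or post-baseline scan, and that the two rows on missing evaluable assessments apply only to patients without such a death.

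State that the existing rules for two or more missed assessments, new anticancer treatment and withdrawal of consent still apply, with the 126-day note unchanged. One addition is needed: where a patient has no evaluable scan at all, the note has no starting point, so count the 126 days from first dose in that case only.

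The cost is two or three sentences, with no new data and no extra analyses. The downside is that the reported PFS rate may be slightly lower than under the censoring reading.

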### **2.2.2 Primary Endpoint**

The primary endpoint is PFS rate.

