## 6.4 Efficacy Assessments

### Tumor Assessment

All measurable and evaluable lesions should be assessed and documented at screening and re-assessed at each subsequent tumor evaluation (see [Appendix A](#)). Assessments should include computed tomography (CT) scans with oral or IV contrast (unless contraindicated) of the chest, abdomen, and pelvis. MRI scans are allowed if CT contrast is contraindicated. Other methods of assessment should be utilized as clinically indicated.

**Tumor assessments for dose escalation cohorts, Dose Expansion Cohort C, Dose Expansion Cohort D, and Dose Expansion Cohort E** are scheduled at Screening and every 8 weeks ( $\pm$ 1 week) thereafter, ie, C3D1, C5D1, C7D1, etc. (odd-numbered cycles).

**Tumor assessments for Dose Expansion Cohort A and Dose Expansion Cohort B** are scheduled at Screening, C2D1, C3D1, C4D1, and every 8 weeks ( $\pm$ 1 week) thereafter, ie, C6D1, C8D1, C10D1, etc. (even-numbered cycles).

Subjects who permanently discontinue study drug for reasons other than progression of disease should continue to be followed for efficacy according to the schedule in [Appendix A](#).

All subjects are to have tumor assessments performed at the Treatment Completion visit, unless the subject was discontinued from treatment because of disease progression or the subject had tumor assessments performed within 14 days of the last dose of study drug.

At the investigator's discretion, CT scans may be repeated at any time if progressive disease is suspected.

Disease status will be assessed using RECIST Version 1.1 (see [Appendix C](#)). The same imaging procedure used to define measurable lesions at baseline must be used throughout the study for each patient.

At the investigator's discretion, other methods of assessment of measurable disease as per RECIST may be used. Examples of other assessment methods include tumor markers, such as prostate-specific antigen (PSA) and cancer antigen 125 (CA-125) levels for patients with prostate and ovarian cancer, respectively. However, tumor markers alone cannot be used to assess response. If markers are initially above the upper normal limit, they must normalize for a patient to be considered in complete response.

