## 8.5 Efficacy Analysis

The efficacy endpoints include PFS, ORR, DCR, and OS. Efficacy data will be listed and summarized by dose cohort and disease type.

The ORR and DCR will be summarized with percentages and 95% exact confidence intervals. The PFS rate at week 12 (Cohorts B and C) and week 16 (Cohorts D and E) and its 95% confidence intervals will be estimated by the Kaplan-Meier method. PFS, DoR, and OS will be summarized descriptively using Kaplan-Meier medians and quartiles. Percentage change in tumor size from baseline will be determined for patients with measurable disease at baseline and derived at each visit by the percentage change in the

sum of the diameters of target lesions (TLs) compared to baseline. Best percentage change in tumor size will be summarized using descriptive statistics and presented using a waterfall plot.

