Date Procedure	Screening		Treatment 							Treatment Completion 	Follow-up
			Cycle 1				Cycle 2-3		Cycle 4 and onwards		
	Day -28 to Day -1	Day -7 to Day -1	Day 1	Day 8 (±1d)	Day 15 (±1d)	Day 22 (±1d)	Day 1 (±3d)	Day 15 (±3d)	Day 1 of each subsequent cycle (±3d)	30 (±7) days after permanent treatment discontinuation	Every 12 (±2) weeks from Treatment Completion Visit
			specific timepoints								
Adverse event 	X	X	X	X	X	X	X	X	X	X	
Fruquintinib treatment			Once daily, 3 weeks on/ 1 week off								
Survival follow up 											X

Note:

1. A written informed consent form should be obtained prior to any protocol-specific procedure or test. Tests completed within 28 days prior to enrollment can be used for screening and do not need to be repeated (except hematology, coagulation test, clinical chemistry, or urinalysis results).
2. Unless otherwise indicated, the visit window during the treatment period will be ± 3 days (± 1 day during cycle 1).
3. Patients who complete or prematurely discontinue the study need to return to the study site for a follow-up at 30 (±7) days after the decision to discontinue treatment permanently. Ongoing AEs will be followed until the event has resolved to baseline grade, the event is assessed as stable by the investigator, new anti-tumor treatment is initiated, the patient is lost to follow-up, the patient withdraws consent, or when it has been determined that the study treatment or participation is not the cause of the AE.
4. The treatment completion visit tumor assessment can be omitted if treatment ended because of disease progression or the patient had a tumor assessment within 14 days prior to the last dose of study drug.
5. Concomitant medication includes any prescribed or over-the-counter medicines. All medication used by patients within 7 days before screening and 30 days after study treatment completion should be recorded. At each visit, all medication used since the prior visit should be recorded.

6. Vital signs include blood pressure, heart rate, respiratory rate, and temperature. For patient with a baseline history of antihypertensive medications, blood pressure should be monitored at 3 hours ( $\pm 2$  hours) after the daily doses of anti-hypertensive medication.
7. Please refer to Section 6.3.2 for the assessments that should be completed as part of the Complete and Limited Physical Exams.

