4.4. EFFICACY ANALYSIS SET [EAS]

This analysis set includes all patients who have received at least 1 dose of fruquintinib, have a measurable lesion (target lesions ≥ 10 mm) at the baseline tumor assessment, and either (i) have had at least one post-baseline tumor assessment, or (ii) do not have post-dose tumor assessment but have clinical progression as noted by the investigator, or have died due to disease progression before their first post-baseline tumor scan. All efficacy endpoints (i.e. BOR, ORR, DCR, DoR, and best percentage change from baseline in tumor size), not including PFS and OS, will be summarized based on this analysis set.

Document: [REDACTED]

Author: [REDACTED]

Version Number: 2.5

Version Date: 18Feb2022

Template No.: [REDACTED]

Reference: CS_WI_BS005

Effective Date: 02Dec2019

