16.2. ANALYSIS OF EFFICACY VARIABLE(S)

The efficacy endpoints include ORR, DCR, DoR, PFS and OS. Efficacy data will be listed and summarized by dose cohort (only in dose escalation phase) or tumor specific cohorts (only in dose expansion phase) and disease type if applicable.

ORR, DCR, and DoR

The ORR and DCR will be summarized with percentages and 95% exact Clopper-Pearson confidence interval based on EAS.

DOR will be summarized using Kaplan-Meier method, and the descriptive statistics of median, 25% and 75% percentiles along with their 95% CIs will be calculated. It will be based on the EAS. The supportive data listings will also be provided.

PFS, OS, and Duration to Follow-Up

PFS and OS will be similarly summarized as DOR, and in addition to the quartile summary from Kaplan-Meier method, Kaplan-Meier estimates will be provided for the rates at 12, 16, 20, and 24 weeks along with their 95% CIs based on the Brookmeyer and Crowley method (1982).

In addition, duration (months) to follow-up for overall survival would be summarized by Kaplan-Meier method. Duration to follow-up refers to the time interval between date of first study drug administration and last date known to be alive for subjects who have not yet been reported to have died by the time of analysis, i.e. (date of last known to be alive – date of first study drug administration + 1)/ 30.475. Subjects who are reported to have died would be censored at death date.

Tumor Shrinkage

Document: [REDACTED]

Author: [REDACTED] Version Number: 2.5
Version Date: 18Feb2022

Template No.: [REDACTED] Reference: CS_WI_BS005

Effective Date: 02Dec2019

Percentage change in tumor size from baseline will be determined for patients with measurable disease at baseline and derived at each visit by the percentage change in the sum of the diameters of target lesions (TLs) compared to baseline. Best (minimum) percentage change from baseline (PCFB) in tumor size will be summarized using descriptive statistics and a waterfall plot will be presented also. Best post-baseline sum of diameter is defined as the sum of diameter with either the largest decrease or smallest increase from baseline sum of diameter at a single post-baseline evaluable tumor assessment visit before RECIST progression of disease. More details please refer to [section 16.1.7](#).

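### An unscanned clinical progressor is a non-responder in the EAS but, if alive, is censored at first dose for PFS, so the primary PFS rate can be overstated

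*SAP*

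**What the plan says.** For the expansion phase, Protocol 2.2.2 states: "The primary endpoint is PFS rate". Protocol 8.5 defines it: "Progression-free survival rate is defined as the percentage of patients without evidence of progression or death at specific time points". The landmarks there are week 12 (Cohorts B and C) and week 16 (Cohorts D and E). In SAP 16.2, "Kaplan-Meier estimates will be provided for the rates at 12, 16, 20, and 24 weeks". SAP 4.2 bases PFS on all treated patients (the SAS).

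SAP 4.4 requires measurable disease for the EAS. It then admits, besides patients with a post-baseline scan, those who "do not have post-dose tumor assessment but have clinical progression as noted by the investigator". SAP 16.1.2 and 16.1.4 count such a patient as neither a response nor disease control.

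SAP 16.1.5 recognises only RECIST 1.1 progression or death as a PFS event and dates PFS from scans. Table 1 censors at first dose any patient under "No evaluable tumor assessment after first dose of study treatment". It has no row for clinical progression.

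Protocol 6.4 requires a tumor assessment at the Treatment Completion visit "unless the subject was discontinued from treatment because of disease progression". Appendix A note 4 agrees: "The treatment completion visit tumor assessment can be omitted if treatment ended because of disease progression". Neither says whether the progression must be radiological. Protocol 3.6 defines progression as a reason to end treatment by RECIST 1.1.

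**The concern.** The plan expects patients who fail clinically before a scan, because SAP 4.4 was changed from the protocol to admit them to the EAS. For response and disease control they are failures. For the primary endpoint they leave the risk set on day 1, which Kaplan-Meier treats as though their outlook matched that of the patients still followed. They were withdrawn because their disease was judged to be worsening, so that assumption is hard to defend.

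The exposure is not trivial. Cohorts C, D and E have no scheduled scan before week 8 (±1 week). SAP 16.2 plans no sensitivity analysis of PFS that would show the effect. The design is single-arm, so no concurrent control group shares the same error.

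**Working it through.** Inputs:

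- Cohort sizes: N = 40 (B, C) and N = 15 (D, E), Protocol 8.6.
- Estimator: Kaplan-Meier rate at the landmark, Protocol 8.5 and SAP 16.2.
- Scoring: SAP 16.1.5 Table 1.
- k, the number of living, unscanned clinical progressors before the landmark: an assumption, since the documents give no figure.
- True rate: here, the rate when clinical progression counts as failure.

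**Step 1: the plan's own figures.** All 12 rows of Protocol Tables 15 and 16 reproduce to two decimals as exact Clopper-Pearson limits. For example, 20/40 gives 0.338 to 0.662, and 6/15 gives 0.163 to 0.677. For tabulated rates other than 0 and 1, the distance from estimate to limit is 7.2 to 16.2 points at N = 40 and 15.7 to 28.1 points at N = 15, as the text states. The sample-size tables are unaffected; they give a scale for what follows.

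**Step 2: censoring at first dose.** Let E patients be event-free at the landmark, with no other censoring before it. The true rate is E/N. Table 1 removes k failures from the risk set on day 1, so Kaplan-Meier returns E/(N − k).

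| N | True rate | k | Reported | Rise (points) |
|---|---|---|---|---|
| 40 | 20/40 = 50% | 1 | 20/39 = 51.3% | 1.3 |
| 40 | 50% | 2 | 20/38 = 52.6% | 2.6 |
| 40 | 50% | 4 | 20/36 = 55.6% | 5.6 |
| 40 | 50% | 8 | 20/32 = 62.5% | 12.5 |
| 40 | 10/40 = 25% | 4 | 10/36 = 27.8% | 2.8 |
| 40 | 30/40 = 75% | 4 | 30/36 = 83.3% | 8.3 |
| 15 | 6/15 = 40% | 1 | 6/14 = 42.9% | 2.9 |
| 15 | 40% | 2 | 6/13 = 46.2% | 6.2 |
| 15 | 9/15 = 60% | 2 | 9/13 = 69.2% | 9.2 |

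At N = 40 and 50%, four such patients move the estimate by about a third of the distance to the 95% limit (5.6/16.2 = 0.35). At N = 15 and 40%, two move it by about a quarter of the distance to the nearer limit (6.2/23.7 = 0.26).

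**Step 3: deaths.** Table 1 also scores a death with no prior progression as an event. Its note on missed assessments allows 126 days, counted from baseline if no later scan exists. Take N = 40, E = 20, k = 4, and suppose that the death row prevails over the no-scan row.

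- If d of the four die before the landmark, the rate is 20/(40 − (4 − d)): 55.6%, 54.1%, 52.6%, 51.3% and 50.0% for d = 0 to 4. The bias shrinks to zero.
- If m of the four die after week 12 but within 126 days, they are event-free at week 12. The rate is (20 + m)/(40 − (4 − m)), rising from 55.6% (m = 0) to 24/40 = 60.0% (m = 4).

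On both paths the error is upward or zero. The SAP does not say which row prevails.

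**Step 4: clinical progression after an earlier scan.** Without a later RECIST progression or a countable death, such a patient is censored at that scan. Kaplan-Meier passes the patient's weight to those still at risk, so the error is again upward or zero. Its size depends on timing, which the formula in Step 2 does not cover.

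**The case against.** The strongest reply is that PFS is defined consistently. Protocol 8.5 and SAP 16.1.5 both require objective progression or death, and declining to count an unscanned judgement is a legitimate choice. This stands, and it is why the RECIST analysis should remain primary. It does not make the censoring uninformative.

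The second reply concerns the exit scan. A reader might infer that clinical progressors are plainly excused from it. The documents do not support that. Under section 3.6, progression as a stopping reason means RECIST progression. A patient stopped on clinical judgement would then fall under another reason, still owe the exit scan and continue efficacy follow-up under 6.4. Section 6.4 also allows a CT whenever progression is suspected. So the waiver is ambiguous, not open. Even on the narrower reading the gap is not fully closed. The exit visit falls 30 (±7) days after the decision to stop, and Table 1 censors a patient who starts new anticancer therapy first, even if that scan then shows progression.

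Third, a reader might infer that every clinical progressor is a failure for ORR and DCR yet censored for PFS. That is too broad. A confirmed response, or stable disease after at least 49 days (SAP Appendix 3), remains a DCR success. Patients with only bone lesions and no measurable disease are outside the EAS. Some patients die or have a later progression scan in time and become PFS events.

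Finally, no benchmark or hypothesis is set (SAP 5.5), and the documents do not show whether any outside study counted clinical progression. A bias against an external comparator is therefore not established.

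**Conclusion.** The inconsistency is real but narrow. A living, unscanned clinical progressor with measurable disease counts against the drug in the EAS and is censored at first dose in the primary analysis. The PFS rate can be overstated and, on the paths checked, is not understated.

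It would go too far to say that the rate is overstated, or by a fixed amount. The illustrative rises of 5.6 points (4 of 40) and 6.2 points (2 of 15) rest on assumed counts, assumed true rates, no other early censoring and no rescue by death or a later scan. With no such patients, or if all die as events before the landmark, the bias is zero.

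One tempting calculation should not be used. An exponential curve with the FRESCO median of 3.71 months gives exp(−ln 2 × (84/30.4375)/3.71) = 59.7% at week 12. Losing 10% on day 1 would turn this into 0.597/0.90 = 66.3%. Cohort C is scanned at weeks 8 and 16, so its scan-dated curve at week 12 need not show either value.

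**What to change.** (a) Reconcile Protocol 6.4 and Appendix A note 4 with section 3.6 by stating that the exit-scan waiver applies only to progression already documented by RECIST 1.1. This settles which scans feed the endpoint; it does not touch when treatment stops.

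(b) In SAP 16.1.5 and 16.2, keep the RECIST analysis as primary. Add a pre-specified supportive PFS rate per cohort that counts investigator-declared clinical progression as an event on its recorded date. Report the number of such patients beside the primary estimate. This assumes that the date is captured on the CRF.

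(c) State in Table 1 which row takes priority when a patient with no post-dose scan dies.

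The cost is one clarifying clause in two places, one priority rule and one extra Kaplan-Meier run per cohort. The downside is a few exit scans that could have been skipped, and a supportive rate that will be lower wherever such patients occur. If there are none, the two rates coincide.
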